  - Autonomic: sweating, trembling, hunger or palpitations (rapid or irregular heart beat)
  - Neuroglycopenic: confusion, drowsiness, speech difficulty, visual disturbances, odd behaviour, impaired balance or incoordination (reduced ability to coordinate movement)
  - General malaise: headache or malaise (feeling discomfort/unease)
  - Other symptoms?

The Investigator must review the diary data for correct reporting of SMPGs and hypoglycaemic episodes at each contact. If the investigator experiences incomplete data in the diary, the subject must be questioned whether there have been any severe hypoglycaemic episodes since the last visit i.e. any hypoglycaemic episodes where the subject was not able to self-treat. Any severe hypoglycaemic episodes must be reported on a hypoglycaemic episode form.

Low SMPG values for non-severe hypoglycaemic episodes not having a hypoglycaemic episode form completed within 7 days since the SMPG measurement should be reported on a hypoglycaemic episode form with as much information as possible. Novo Nordisk will not query for additional data except for the date, SMPG value and whether the subject was able to self-treat due to decreased validity of such data .

The subject must be re-trained in how to report hypoglycaemic episodes if the investigator identifies unreported hypoglycaemic episodes.

If the hypoglycaemic episode fulfils the criteria for an SAE then an AE form and a safety information form must also be filled in (see section [12](#)).

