## 12 Adverse events, and technical complaints and pregnancies

### 12.1 Definitions

#### Adverse event

An AE is any untoward medical occurrence in a subject administered a product, and which does not necessarily have a causal relationship with this treatment.

An AE can therefore be any unfavourable and unintended sign (including an abnormal laboratory finding), symptom or disease temporally associated with the use of a product, whether or not considered related to the product.

An AE includes:

- A clinically significant worsening of a concomitant illness.
- A clinical laboratory adverse event (CLAE): a clinical laboratory abnormality which is clinically significant, i.e. an abnormality that suggests a disease and/or organ toxicity and is of a severity that requires active management. Active management includes active treatment or further investigations, for example change of medicine dose or more frequent follow-up due to the abnormality.

The following should **not** be reported as AEs:

- Pre-existing conditions, including those found as a result of screening procedures (pre-existing conditions should be reported as medical history or concomitant illness).
- Pre-planned procedures unless the condition for which the procedure was planned has worsened from the first trial related activity after the subject has signed the informed consent.
- Non-serious hypoglycaemia is an AE, but is reported on a hypoglycaemic episode form instead of on an AE form, see section [8.4.1.1](#).

The following three definitions are used when assessing an AE:

- **Severity**
  - **Mild** - no or transient symptoms, no interference with the subject's daily activities.
  - **Moderate** - marked symptoms, moderate interference with the subject's daily activities.
  - **Severe** - considerable interference with the subject's daily activities; unacceptable.
- **Causality**

Relationship between an AE and the relevant trial product(s):

- **Probable** - Good reason and sufficient documentation to assume a causal relationship.
- **Possible** - A causal relationship is conceivable and cannot be dismissed.
- **Unlikely** - The event is most likely related to aetiology other than the trial product.

- **Final outcome**

- **Recovered/resolved** - The subject has fully recovered, or by medical or surgical treatment the condition has returned to the level observed at the first trial-related activity after the subject signed the informed consent.

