## **12.2 Reporting of adverse events**

All events meeting the definition of an AE must be collected and reported. This includes events from the first trial-related activity after the subject has signed the informed consent until the end of the post-treatment follow-up period (Visit 38). The events must be recorded in the applicable eCRF forms in a timely manner, see timelines below and [Figure 12-1](#).

During each contact with the trial site staff, the subject must be asked about AEs and technical complaints, for example by asking: "Have you experienced any problems since the last contact?"

All AEs, either observed by the Investigator or subject, must be reported by the Investigator and evaluated. Novo Nordisk assessment of expectedness is performed according to the following reference documents:

- Faster-acting insulin aspart: Faster-acting insulin aspart IB. Current version and any updates hereof
- NovoRapid®: Company Core Data Sheet. Current version and any updates hereof
- Insulin degludec: Insulin degludec IB. Current version and any updates hereof

All AEs must be recorded by the Investigator on an AE form. The Investigator should report the diagnosis, if available. If no diagnosis is available, the Investigator should record each sign and symptom as individual AEs using separate AE forms.

For SAEs, a safety information form must be completed in addition to the AE form. If several symptoms or diagnoses occur as part of the same clinical picture, one safety information form can be used to describe all the SAEs.

MESIs, regardless of seriousness, must be reported using the AE form, the safety information form and a MESI form. The MESI form is a form tailored to collect specific information related to the individual MESI.

The AE form for a non-serious AE not fulfilling the MESI criteria should be signed when the event is resolved or at the end of the trial.

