### 18.1 Benefit-risk assessment of the trial

All subjects included in the trial will be treated with insulin degludec as basal insulin in addition to either NovoRapid® or faster-acting insulin aspart. Insulin degludec will be titrated weekly by the Investigator during the initial 8-week run-in period. The bolus insulin will be adjusted daily or weekly during the treatment period of the trial depending on the methods used by the subject to adjust their bolus dose.

The most common side effect of all available insulin preparations is hypoglycaemia. The Investigator will explain to the subject how they should check their BG with the BG meter provided by Novo Nordisk and what precautions to take.

Subjects randomised in the trial will be transferred to a treatment regimen anticipated to be either better than or equal to the treatment they received at the time they entered the trial. However, subjects will have to use extra time as additional visits to the clinic are required and some of the assessments performed during the trial are done outside normal practice.

When treatment with trial products ends, the subject and Investigator will decide on the best available treatment on the market. It will not be possible for the subjects to continue using faster-acting insulin aspart or insulin degludec trial products.

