## **2.16 Section 8.1.13 Premature discontinuation of trial product**

*If a subject is prematurely discontinued from trial product after randomisation (Visit 10), the Investigator must ensure every possible effort is made to undertake procedures for Visit 36A, as soon as possible.*

*Treatment discontinuation must be performed in the eDiary web portal. This must be performed at least 4 days prior to Visit 36A to ensure scheduling of the 7-9-7-point profile on the three days prior to Visit 36A.*

*At visit 36A subjects must undergo the meal test before discontinuing trial product. The meal test should be performed with trial drug according to randomisation unless this is not feasible due to safety reasons including pregnancy as judged by the investigator. This must be documented in the eCRF.*

*A "treatment discontinuation" session must be made in the IV/WRS after the meal test has been completed and primary reason for discontinuation of trial product must be specified in the first part of the end-of-treatment/trial form in the eCRF.*

*Final drug accountability must be performed. The subject should be switched to a suitable marketed product at the discretion of the Investigator. The medication should be recorded on the concomitant diabetes medication form in the eCRF, as described in section 8.2.4 at each contact after trial drug discontinuation.*

*The subject should also complete the follow-up visits (visit 37 and phone contact 38). Visit 37 can be converted into a phone contact as collection of the eDiary is not applicable at this visit for the subjects that discontinue trial product prematurely.*

*In addition, subjects prematurely discontinued from trial product should continue with the per protocol planned visits at 4 (Visit 14), 8 (Visit 18), 12 (Visit 22), 16 (Visit 26), 20 (Visit 30), 24 (Visit 34) and 26 (Visit 36) weeks after randomisation depending on when the subject discontinues trial product. The meal test at V36 should be done with the subjects' currently prescribed insulin treatment with a bolus insulin dose of 0.1 U/kg. The eDiary must be returned to the site at the end of visit 36.*

*The following assessments are not applicable for subjects that prematurely discontinue trial product: 4 point profiles, daily doses of trial insulin, time of injection, duration of meal, titration method, dose recommendation, reason for deviation and collection of technical complaints.*

*In the following situations, only one visit should take place:*

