## **2.25 Section 12 Adverse events, and technical complaints and pregnancies**

### **2.25.1 Section 12.1 Definitions**

#### **Adverse event**

An AE is any untoward medical occurrence in a subject administered a product, and which does not necessarily have a causal relationship with this treatment.

An AE can therefore be any unfavourable and unintended sign (including an abnormal laboratory finding), symptom or disease temporally associated with the use of a product, whether or not considered related to the product.

An AE includes:

- A clinically significant worsening of a concomitant illness.
- A clinical laboratory adverse event (CLAE): a clinical laboratory abnormality which is clinically significant, i.e. an abnormality that suggests a disease and/or organ toxicity and is of a severity that requires active management. Active management includes active treatment or further investigations, for example change of medicine dose or more frequent follow-up due to the abnormality.

The following should **not** be reported as AEs:

- Pre-existing conditions, including those found as a result of screening procedures (pre-existing conditions should be reported as medical history or concomitant illness).
- Pre-planned procedures unless the condition for which the procedure was planned has worsened from the first trial related activity after the subject has signed the informed consent.
- Non-serious hypoglycaemia is an AE, but is reported on a hypoglycaemic episode form *in the eDiary* instead of on an AE form, see section 8.4.1.1.

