### **Number of treatment emergent Adverse Events AEs during 26 weeks of treatment**

AEs will be coded using the Medical Dictionary for Regulatory Activities (MedDRA). ~~All~~ AEs ~~occurring during the 26 weeks of treatment~~ will be presented based on system organ class and preferred terms.

A Treatment Emergent Adverse Event (TEAE) is defined as an event that has an onset date on or after the first day of exposure to randomised treatment, and no later than seven days after the last day of treatment.

TEAEs are summarised descriptively, whereas AE's not defined as treatment emergent are presented in listings, including AEs reported in the 30-day follow-up period. The summaries of TEAEs are made displaying the number of subjects with at least one event (N), the percentage of subjects with at least one event(%), the number of events(E) and the event rate per 100 patient years of exposure(R). These summaries are done by seriousness, severity, relation to insulin treatment, relation to device, ~~withdrawal~~ premature treatment discontinuation due to AEs and outcome.

Furthermore, summary tables based on system organ class and preferred terms are made for:

- all TEAEs
- serious TEAEs
- possibly or probably related TEAEs
- severe TEAEs
- TEAEs with preferred term that are experienced by at least 5% of the subjects in any treatment arm or by at least 5% of all subjects

For AEs where additional information is recorded, this will be summarised and listed.

AEs occurring during the run-in period are considered non treatment emergent and will be summarised separately.

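### A subject who stops trial product because of non-serious hypoglycaemia has no stated route into the summary of discontinuations due to adverse events

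*Protocol*

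**What the plan says.** **Reporting route.** Section 12.1 of the protocol, under events not to be reported as AEs, states: "Non-serious hypoglycaemia is an AE, but is reported on a hypoglycaemic episode form instead of on an AE form". Amendment 2 restates section 12.1 with the same rule and adds that the form is in the eDiary. Section 12.2 says, with no exception: "All AEs must be recorded by the Investigator on an AE form".

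**Cases that do get an AE form.** Section 8.4.1.1: "If the hypoglycaemic episode fulfils the criteria for an SAE then an AE form and a safety information form must also be filled in". Section 12.2: "MESIs, regardless of seriousness, must be reported using the AE form, the safety information form and a MESI form". In this trial the criteria for a medical event of special interest (MESI) are medication errors with trial product.

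**Planned summary.** Amended section 17.4.2.2 summarises treatment-emergent AEs by seriousness, severity, relation to insulin treatment and to device, and then by "premature treatment discontinuation due to AEs and outcome". The same section gives hypoglycaemia its own tables, by classification, time of day and time since meal.

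**Reason for stopping.** New section 8.1.13 (Amendment 2) requires that the "primary reason for discontinuation of trial product must be specified in the first part of the end-of-treatment/trial form in the eCRF".

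**Relevance.** Section 18.1: "The most common side effect of all available insulin preparations is hypoglycaemia".

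**The concern.** Discontinuation due to AEs is one of the figures a reader uses to judge tolerability. For an insulin, hypoglycaemia is an obvious event to look for there. The protocol calls non-serious hypoglycaemia an AE, yet keeps it off the form on which AEs are assessed. If an investigator takes a subject off trial product because of repeated non-serious episodes, no event record described in the protocol carries that consequence.

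The gap is not confined to trivial episodes. An episode in which another person had to help is severe under the ADA classification, but it gets an AE form only if it also meets an SAE criterion, or if it qualifies as a medication error.

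At stake is the completeness of one descriptive safety breakdown, and its agreement with the reasons on the end-of-treatment/trial form.

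**Working it through.** The plan states no figure for discontinuations due to hypoglycaemia, so there is nothing to reproduce. The check is to follow one case through the text and then set a scale.

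**Step 1: which form is completed.** Take a randomised subject with repeated non-serious episodes, no SAE criterion met and no medication error. Under section 12.1 (original and amended), only the episode form applies. The general sentence in 12.2 would call for an AE form too. Read together, 12.1 is the specific rule and 12.2 the general one, so a site would most naturally complete the episode form alone.

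**Step 2: what that form holds.** Section 8.4.1.1 has the subject complete it. The two sets of items compare as follows.

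| Attribute used in the TEAE summary (amended 17.4.2.2) | Listed for the episode form (8.4.1.1)? |
|---|---|
| Severity (mild/moderate/severe, defined in 12.1) | No; only whether the subject could self-treat, with further items if not |
| Relation to insulin treatment | No |
| Outcome (categories in 12.1) | No; only whether symptoms eased after assisted treatment |
| Discontinuation due to AE | No |

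**Step 3: whether the hypoglycaemia tables fill the gap.** Section 17.4.2.2 presents subjects, percentages, events and rates, overall and by class, day or night, and interval after a meal. It adds a negative binomial analysis of severe or BG confirmed episodes. None of these is broken down by discontinuation.

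**Step 4: where the reason is held.** It is on the end-of-treatment/trial form, as one primary reason (amended 8.1.13). Nothing in section 17 links that form to the TEAE summary. The surveillance of reasons in amended section 19.1 is operational and is not an analysis.

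**Step 5: whether the case is foreseeable.** Amended section 6.6 allows the investigator to discontinue trial product for a safety concern, so the plan itself admits the case.

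**Step 6: scale.** Amended section 17.1 says treatment discontinuation might be as low as 8%, with 999 subjects, 333 per arm.

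- Expected discontinuers: 0.08 × 999 = 79.9, about 80; per arm 0.08 × 333 = 26.6, about 27.
- The share due to non-serious hypoglycaemia is not given. Assume 0% to 20%.
- Overall: 0 × 79.9 = 0 to 0.20 × 79.9 = 16.0 subjects. Per arm: 0 to 0.20 × 26.6 = 5.3, about 5.
- Intermediate values overall: 5% gives 4.0 and 10% gives 8.0.

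**The case against.** The strongest reply is that nothing is lost. The protocol calls these episodes AEs, defines a treatment-emergent AE by its onset date and not by the form used, and names no data source for the discontinuation breakdown. The reason for stopping is collected for every subject who discontinues after randomisation. Which dataset feeds which table is normally SAP business. The protocol does not list an item on action taken with trial product for the AE form either.

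Much of this stands. A reader might infer that the planned count definitely excludes these subjects, or that the end-of-treatment reason cannot be used in it. The documents say neither. Nor do they support a claim that non-serious hypoglycaemia never reaches an AE form, because medication-error episodes do.

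The conflict between 12.1 and 12.2 is also mild: a specific carve-out beside a general sentence.

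What does not fall away is the data-collection rule. Whether the investigator completes an AE form is fixed in the protocol. An SAP can decide to count the end-of-treatment reason, but it cannot recover a causality or outcome assessment that was never requested.

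It can also be said that hypoglycaemia is analysed thoroughly elsewhere, so an imbalance in episodes between arms would show. That is true, but those tables do not show who stopped because of them.

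**Conclusion.** The point holds in a limited form. For non-serious hypoglycaemia that meets no MESI criterion, the protocol provides no stated route from the event to the summary of discontinuations due to AEs. The reason sits on a different form, and the two sources may disagree.

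The size is unknown. The 0 to about 16 subjects rest on an assumed share and on a discontinuation rate that the plan itself gives only as a possible low value; the true number could be zero. Discontinuation due to AEs is not among the endpoints in section 4.2.2.2. The affected table is descriptive, and no step of the testing hierarchy depends on it.

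A reader might also infer a bias between arms, because section 3.3 reports a higher hypoglycaemia rate in the first hour after a meal with faster-acting insulin aspart in an earlier trial. The same section reports no significant difference in the overall rate and describes the first-hour episodes as a smaller fraction. This shows only that equal omission across arms cannot be taken for granted. It does not show an unequal one.

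**What to change.** 1. In sections 12.1 and 8.4.1.1, require an AE form in addition to the episode form when hypoglycaemia is the reason for premature discontinuation of trial product. All other non-serious hypoglycaemia stays on the episode form only, apart from MESI cases.
2. In section 17.4.2.2, state that these subjects count as discontinued due to AEs, and that the count is reconciled with the primary reason on the end-of-treatment/trial form.
3. In section 12.2, add an exception referring to 12.1 to the sentence on AE forms.

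This changes reporting only and leaves treatment and stopping rules as they are. The two-form approach already exists in the protocol: section 8.4.1.2 asks for both an AE form and a special form for injection site reactions.

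The cost is three short text changes and a few extra AE forms. The discontinuation figure may come out slightly less favourable.

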### **Serious adverse event**

A SAE is an experience that at any dose results in any of the following:

- Death.
- A life-threateninga experience.
- In-patient hospitalisationb or prolongation of existing hospitalisation.
- A persistent or significant disability or incapacityc.
- A congenital anomaly or birth defect.
- Important medical events that may not result in death, be life threateninga or require hospitalisationb may be considered an SAE when - based on appropriate medical judgement - they may jeopardise the subject and may require medical or surgical intervention to prevent one of the outcomes listed in the definition of SAEd.

Suspicion of transmission of infectious agents via the trial product must always be considered an SAE.

a. The term "life threatening" in the definition of SAE refers to an event in which the subject was at risk of death at the time of the event. It does not refer to an event which hypothetically might have caused death if it was more severe.

b. The term "hospitalisation" is used when a subject:

- Is admitted to a hospital or in-patient, irrespective of the duration of physical stay, or
- Stays at the hospital for treatment or observation for more than 24 hours

Medical judgement must always be exercised, and when in doubt, the hospital contact should be regarded as a hospitalisation. Hospitalisations for administrative, trial related and social purposes do not constitute AEs and should therefore not be reported as AEs or SAEs. Hospital admissions for surgical procedures, planned before trial inclusion, are not considered AEs or SAEs.

- c. A substantial disruption of a subject's ability to conduct normal life functions (e.g. following the event or clinical investigation the subject has significant, persistent or permanent change, impairment, damage or disruption in his/her body function or structure, physical activity and/or quality of life).
- d. For example intensive treatment in an emergency room or at home of allergic bronchospasm, blood dyscrasiasis or convulsions that do not result in hospitalisation, or development of drug dependency or drug abuse.

### **Non-serious adverse event**

A non-serious AE is any AE which does not fulfil the definition of an SAE.

### **Medical event of special interest**

A MESI is an event which, in the evaluation of safety, has a special focus. A MESI is an AE (SAE or non-serious AE) which fulfils one or more of the below defined MESI criteria.

1. Medication errors concerning trial products:
  - Administration of wrong drug
    - For patients treated in the mealtime arms (blinded product) use of wrong DUN is not considered a medication error.
    - For patients treated in run-in and postmeal arm (open label) use of wrong DUN is not considered a medication error unless it results in administration of wrong drug
  - Wrong route of administration, such as intramuscular instead of subcutaneous.
  - Administration of an overdose with the intention to cause harm (e.g. suicide attempt).
  - Accidental administration of a lower or higher dose than intended i.e. dose which may lead to significant health consequences, as judged by the Investigator, irrespective of whether the SAE criteria are fulfilled or not.

